7.2.4. Complete blood count (CBC)

Blood counts measured by standard CBC with differential procedures will be abstracted from the patient's medical record.

7.2.5. Muscle mass testing

The RJL Bioelectrical Impedance System is a non-invasive, easy-to administer and safe method of assessing lean body mass. BIA involves passing a small electrical current through the body and evaluating the reactance and resistance to flow, which are related to fat-free mass (FFM) and total body water. Prediction of lean body mass from BIA is as reliable as skin-fold measurements and hydrostatic weighing. Participants have the option to be 4 hours fasted, although it is not required. Participants need to be abstained from alcohol and diuretics (unless prescribed) for 48 hours, well hydrated (water only), and voided completely prior to assessment. Participants lie supine on a flat surface for approximately 5 minutes prior to the test, to ensure a resting metabolic state. Electrodes are attached to the right hand (proximal phalanx of the 3rd finger and the radiocarpal joint), and the right foot (distal end of the 3rd and 4th metatarsal and distal end of the tibia and fibula). Skeletal muscle mass will then be calculated from the lean body mass.

7.2.6. Muscle strength testing

Upper extremity muscle strength will be assessed using a handgrip dynamometer.¹⁰⁴

The Handgrip Dynamometer Test is a grip strength test used to assess the maximal voluntary contraction generated by the arm muscles. The test is administered with the patient standing in anatomical position; the elbow joint angle will be held constant at 90 degrees with the medial distal humeral epicondyle held 2 inches from the torso. Trials will be performed in an alternating bilateral sequence for a total of six attempts (three with each arm). The best score of the three trials will be used for right and left limbs to calculate static strength. The surgically involved arm(s) will be noted for data analysis. The handgrip dynamometer test has been previously used in a number of URCC NCORP protocols and has shown to be a reliable clinical method of assessing upper extremity strength.

Lower and upper extremity muscle strength will be assessed using the isokinetic muscular strength test. We will use an isokinetic knee flexion/extension for lower extremities and seated shoulder diagonal for upper extremities. If seated shoulder diagonal cannot be performed (e.g., prior shoulder injury), elbow flexion/extension will be performed instead. An exercise physiologist will provide a full orientation to the isokinetic machine including: aligning subject into position, setting range of motion, and conducting a warm up set. The exercise physiologist will be present during the test to ensure proper form and subject comfort. After the warm up set, subjects will complete a single set per side. Subjects will exert maximal force through their entire range of motion, moving at a set speed in degrees per second against the lever arm. Subjects will rest for approximately 3 minutes between sets. This isokinetic protocol will allow us to measure peak torque, maximal work, total work, and average power for each movement. We will use a Biodex System 4 Pro, which has been used successfully in over 1,000 research studies and is both safe and accurate in measuring muscular function.¹²⁰

Muscle activation during strength testing (isokinetic muscular strength test) will be assessed using electromyography sensors. The BTS FREEEMG 1000 is a wireless EMG system that directly measures muscle activity. The system uses eight miniaturized probes with active electrodes for signal acquisition and transmission for EMG, angles, speed, acceleration, and pressure assessment. The probes include on-board memory. The subject will have full range of motion during task execution. BTS FREEEMG can measure the movement of any muscle activity, is analyzed by the BTS EMG-Analyzer software, and integrates with the BioDex. Probes will be applied to subject's skin surface over the muscle used during knee flexion and extension and elbow flexion extension repetitions. Height and weight will be assessed using the Blue Bell Bio-Medical SR Instruments Model 500. We will also measure waist circumference with a Gulick tape measure. Height, weight, and waist circumference will be assessed at each PEAK lab visit to help estimate body composition. Waist circumference will be measured from the narrowest portion above the umbilicus and below the zyphoid process.

7.2.7. Heart Rate Variability (HRV): HRV measures variation in consecutive heartbeat intervals. It provides acute measures of physiological recovery. HRV data will be collected for 5 minutes and assessed using the Firstbeat® system. Firstbeat® is a portable device consisting of two electrodes (one above and below the ribcage) placed on the patient.

7.3. Post-Intervention Assessment of the Participants

At the post-intervention assessment, all subjects will continue to wear their Garmin activity tracker for 4-7 days. Study staff will collect the tablet from the participants. Participants will keep the EXCAP exercise kit. In addition to the assessments above, we will assess the intervention usability. We will also conduct an exit interview either inperson or via zoom/phone to elicit app functionality and barriers to adherence to the intervention.

7.3.1. Intervention Usability^{105,106}

System Usability Scale is a standardized questionnaire used to assess participants' perceptions of usability. This robust and reliable scale consists of a 10-item questionnaire with each item rated on a 5-point Likert scale (see Appendix). The scores for each question will be converted to a new number (odd-numbered questions are calculated as the scale position minus 2, and even-numbered questions are calculated as 5 minus the scale position), added together, and then multiplied by 2.5 to get the final score (ranging from 0 to 100).

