The feasibility of the GO-EXCAP Mobile App will be evaluated based on the following: a) Percentage of patients wearing the activity tracker and entering resistance exercise data into the mobile app and b) Percentage of patients performing both walking and resistance exercises during the study period days. Recruitment rates (percentage of patients who are approached and agree to enroll) and retention rates (percentage of patients who are enrolled and complete post-intervention assessments) will also be described

We will consider the intervention feasible if 1) \geq 70% of patients wear the activity tracker and enter resistance exercise data into the mobile app on at least 50% of the study period days, and 2) \geq 70% of patients performed both walking and resistance exercises on at least 50% of the study period days. We chose these criteria based on our previous mobile app study¹⁶ and on published exercise studies in older patients with AML.^{29,30} We will report percentage of adherence with 95% exact confidence interval (CI) calculated by the Clopper-Pearson method. We anticipate that about 20-30% of the participants will withdraw before post-intervention assessment due to rapid disease progression or death. These patients will not be included in the feasibility analysis because their withdrawals from the study are not related to the intervention. With 25 patients enrolled we anticipate at least 17 patients to be evaluable for our feasibility aims. When we estimate the percentage of adherence, a 95% CI will span approximately +/- 25%. For example, if we observe 12/17 (71%) patients complete the tasks, the CI will be 44-90%.

We will also tabulate the recruitment rates, retention rates, and intervention usability, and collect the reasons patient decline to be enrolled. In addition, we will evaluate the distribution and describe the following measures using descriptive statistics: 1) activity levels, 2) physical function (SPPB/vSPPB), 3) fatigue (BFI), 4) depression (CES-D Scale), 5) quality of life (FACT-Leu), and 6) Other geriatric assessment measures. Differences in activity levels, physical function, fatigue, depression, quality of life, and other geriatric assessment measures between pre- and post-treatment will be assessed using paired t-tests or Wilcoxon signed rank tests. Anticipated sample size of more than 12 patients with baseline and follow-up data will be sufficient to obtain the preliminary estimates of the outcomes measures.^{115,116}

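### The System Usability Scale scoring rule in Section 7.3.1 gives -12.5 to 87.5, not the stated 0 to 100, and would lower every complete score by 12.5 points

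*Combined protocol and SAP*

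**What the plan says.** Section 7.3.1 (Intervention Usability) describes the instrument as one that "consists of a 10-item questionnaire with each item rated on a 5-point Likert scale". It then gives the conversion: "odd-numbered questions are calculated as the scale position minus 2, and even-numbered questions are calculated as 5 minus the scale position". The converted values are added and "multiplied by 2.5 to get the final score (ranging from 0 to 100").

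Section 8.2.2 (Analysis Plan for Aim 2) states how the result will be used: "We will also tabulate the recruitment rates, retention rates, and intervention usability". No threshold, test or target value is attached to usability. The data collection table in Section 9.1 schedules the scale at the post-intervention assessment only, and Section 3.2 describes Aim 2 as a single-arm pilot.

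**The concern.** The two halves of the conversion do not match. Taking 5 minus the position puts an even item on 0 to 4. Taking the position minus 2 puts an odd item on -1 to 3. Ten items on 0 to 4, summed and multiplied by 2.5, would give 0 to 100, but the written rule leaves half of them one point too low.

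At stake is the absolute level of a planned reported outcome. With no control arm and no baseline usability score, the level is the whole result, and a constant error cannot drop out of a difference. The error is also easy to miss. A score comes out negative only when the score on the 0 to 100 scale would be below 12.5. For any other patient the wrong value still lies between 0 and 87.5 and passes a range check. Section 8.2.2 anticipates at least 17 evaluable patients, and in a group of about that size there may be no patient low enough to expose the slip. Readers would then take a figure 12.5 points too low as a score on the stated 0 to 100 scale.

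**Working it through.** **Inputs (all from Section 7.3.1).** Ten items, five odd-numbered and five even-numbered; five response positions, taken as 1 to 5; odd conversion = position - 2; even conversion = 5 - position; multiplier 2.5; stated range 0 to 100.

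**Formula as written.** Let O be the sum of the five odd positions and E the sum of the five even positions, each between 5 and 25.

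Score = 2.5 x [(O - 10) + (25 - E)] = 2.5 x (O - E + 15)

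**Attempt to reproduce the stated range.**

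- Minimum (odd items at 1, even items at 5): 2.5 x (5 - 25 + 15) = 2.5 x (-5) = -12.5
- Maximum (odd items at 5, even items at 1): 2.5 x (25 - 5 + 15) = 2.5 x 35 = 87.5

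The stated 0 to 100 is not reproduced. Enumerating all 5^10 response patterns gives the same two limits.

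**Does the coding of the positions matter?** The section does not say whether the positions are numbered 1 to 5. If they were numbered 0 to 4 or 2 to 6, O and E would move by the same amount and O - E would not change. All three codings give -12.5 to 87.5.

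**With odd items scored as position - 1.**

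Score = 2.5 x [(O - 5) + (25 - E)] = 2.5 x (O - E + 20)

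| Response pattern | As written | Odd items minus 1 | Difference |
|---|---|---|---|
| Worst possible | -12.5 | 0 | 12.5 |
| All neutral (every item at 3) | 37.5 | 50 | 12.5 |
| Best possible | 87.5 | 100 | 12.5 |

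The difference between the two formulas is 2.5 x (20 - 15) = 12.5 for every pattern, and the enumeration confirms this. It equals 5 odd items x 1 point x 2.5.

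**Is that the only repair?** Keeping position - 2 for odd items and using 6 - position for even items gives 2.5 x [(O - 10) + (30 - E)] = 2.5 x (O - E + 20), which is the same total. The 12.5-point shift therefore does not depend on which constant is corrected. Subtracting 1 from odd items is the natural choice because it puts every item on 0 to 4. The alternative leaves odd items on -1 to 3 and even items on 1 to 5.

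**The case against.** The strongest objection concerns weight; the arithmetic is not in dispute. Usability is not one of the four feasibility metrics in Section 2, nor part of the two criteria in Section 8.2.2 by which the intervention will be judged feasible. The data collection table lists it in a separate row from the feasibility metrics. It has no cut-off and plays no part in the sample size. The error is a known constant, so standard deviations, ranks, confidence-interval widths and correlations are unchanged, and adding 12.5 to a complete questionnaire restores the intended score. The section also calls the questionnaire standardized, cites sources for it and refers to an appendix that is not in the text available for this review, so the scoring code may already use a correct rule.

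All of this stands as a limit on the consequences. It means that no decision in the trial turns on the error, and that the loss is conditional: scores are too low only if the written rule is applied. It does not remove the contradiction. The rule and the range stand in one sentence, nothing else in the available text corrects the rule, and an analyst who follows the plan will report wrong values. The shift can be reversed only once someone has noticed it.

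**Conclusion.** The concern holds. The scoring rule in Section 7.3.1 contradicts the range given in the same sentence, and no common renumbering of the five positions reconciles them. If followed, the rule lowers each complete questionnaire, and therefore the mean, by exactly 12.5 points, caps the score at 87.5 and allows negative values.

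The conclusion that the rule and range conflict needs only ten items, half of them odd-numbered, and five consecutive positions. The 12.5-point size also assumes that the stated 0 to 100 range is the intended one. The documents do not show which rule the scoring code uses. The practical effect is confined to the reported usability scores; the feasibility conclusion and the other outcomes are untouched.

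**What to change.** In Section 7.3.1, change the odd-item conversion from the position minus 2 to the position minus 1, and leave the even-item conversion, the multiplier and the range as they are. State that positions are numbered 1 to 5. Check the scoring code and the appendix copy of the questionnaire against the corrected rule. Rescore any questionnaire already scored by the written rule: for a complete one, add 12.5 points; for one with missing items, rescore from the item responses. A useful test for the code is that all-neutral answers must return 50.

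The cost is one digit and a clarifying phrase in the document plus a short code check. No new data are needed.

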7.4. Assessment of inflammatory markers (Exploratory Aim 2)

Using blood samples, we will assess the blood concentrations of several inflammatory markers. All blood draws will occur in the Wilmot Cancer Center, a UR-affiliated lab, or medical office if needed (in the latter case, we will use a trained study staff member to transport the samples to our storage facility). The location will be selected to minimize subject burden and if possible we will perform blood draws at the same time as a regularly scheduled medical blood draws. The blood will be drawn by trained staff. The time of day will be noted, with future assessments at approximately the same time of day during post-testing. Fasted blood samples (4-6 hours prior to blood with encouragement to maintain hydration) will be drawn. If the blood sample is not fasted, we will still

collect the blood sample and note the last time the person ate in the research record. All subjects will be provided with a \$10 gift card for a café at URMC.

A total of approximately 50 mL of blood (around 4-5 tablespoons) will be drawn at baseline and post-intervention. All tubes will be collected by a study team member, processed, and then transferred to a secured -80°C freezer in lab space maintained by [name] in the Department of Surgery. We will collect the following:

- 1. One red-top tube for serum (9 mL each). This tube will be inverted 10 times, allowed to clot for 30 minutes at room temperature, centrifuged for 15 min at 1600 g and then frozen at -20°C or -80°C. These will be used to assess inflammation (cytokines, etc.).
- Two purple-top EDTA tubes for DNA methylation and plasma analyses (9 mL each, 18 mL total). This tube will be inverted 10 times and allowed to sit at room temp for 30 minutes, centrifuged for 15 min, and then frozen at -20°C or -80°C.
- 3. Two green-top tubes for peripheral blood mononuclear cells (9 mL each, 18 mL total). These will be pre-cooled and processed per SOP. This tube will be inverted 10 times and allowed to sit at room temp for 30 minutes, centrifuged for 15 min, and then frozen at -20°C or -80°C.
- 4. Two paxgene tubes for gene expression analyses (2.5 mL each, 5 mL total). This tube will be inverted 10 times and allowed to sit at room temp for 2-24 hours. Then they will be frozen at -20°C and moved to -80°C for long-term storage.

Inflammatory cytokines will be assessed using the latest available technology (e.g., *in vitro* enzyme-linked immunosorbent assay; ELISA). These assays will assess the concentration of inflammatory cytokines including TNF α , sTNFR1, sTNFR2, IL-1 β , IL-6, sIL-6R, IL-8, IL-10. Cytokine analyses will be performed at [name] lab.

For DNA methylation analysis, genomic DNA will be isolated from peripheral mononuclear cells with a DNeasy Blood and Tissue Kit (Oiagen) and quantified with the NanoDrop 1000 spectrophotometer. $TNF\alpha$ gene promoter methylation will be quantified using bisulfite pyrosequencing.¹⁰⁷ Briefly, genomic DNA (1000 ng) will be bisulfite converted (converts cytosine to uracil but leaves 5-methylcytosine residues unaffected) using the Epitect Plus Bisulfite Conversion Kit (Qiagen). Using $TNF\alpha$ -specific primers, the region of interest will be amplified by PCR with the PyroMark PCR kit (Qiagen). Pyrosequencing analysis will be used to measure DNA methylation in the $TNF\alpha$ promoter region from -360 to +50 base pairs (containing 12 CpG sites) using the PyroMark Advanced Q24 (Qiagen).¹⁰⁸ We selected these 12 CpG sites based on a prior study which showed that total methylation and methylation at -245 bp correlated with serum TNFa levels.¹⁰⁸ Methylation at -170bp and -120bp also predicted response to a lifestyle behavioral intervention.¹⁰⁸ In addition, the majority of known regulatory transcription factor binding sites (e.g. NF- κ B, Sp-1, Egr1)¹⁰⁹ within the *TNFa* gene promoter region are located in this region. Other cytokine gene promoter methylation will be analyzed as per $TNF\alpha$ (promoter regions will be determined based on previous studies).^{110–112} DNA methylation analyses will be performed at [name] lab.

For gene expression, RNA will be extracted using the RNeasy Mini Kit (Qiagen) according to the manufacter's protocol and quantified using the NanoDrop spectrophotometer.¹⁰⁷ cDNA will be will be prepared by RT-PCR using Superscript IV reverse transcriptase and random hexamers (Invitrogen). qPCR analysis will be conducted using the Applied Biosystems QuantStudio 5 Real-Time PCR system using *TNFa* and cytokine gene-specific primers. Relative expression of *TNFa* and related genes will be calculated using the comparative Ct method, and measurements will be normalized to expression of two reference genes. Gene expression analyses will be performed at [name] lab.

All human biological materials will be disposed of in adherence with the University of Rochester Office of Environmental Safety Biosafety Level II requirements. All laboratories used in the current study have received appropriate biosafety certifications by the University of Rochester Institutional Biosafety Committee and undergo routine inspections. All samples will be de-identified before being stored.

7.5. Data specimen banking for future research

We will bank blood samples for use in future studies to assess other inflammatory markers and genome wide DNA methylation analysis. We will also keep remaining samples for future research by [name] and her research team. The consent form includes a section asking whether subjects agree to have their samples banked for future studies by [name] and her research team.

Genome wide DNA methylation [with subsequent DNA methylation age (DNAm age analysis) will be performed at Genomic Shared Resource at Roswell Park Cancer Institute. We are in the process of obtaining an MTA with Roswell. After processing, stored blood is aliquoted and identified using study ID. No patient identifiers are included in the label. Aliquotes will be sent to Roswell Park. DNA methylation microarray assay will be performed using the Illumina Infinium® Methylation EPIC Array platform, an oligonucleotide array that interrogates >850,000 CpG dinucleotides per sample, in accordance with the manufacturer's instructions. The raw data will be processed by the R package "minfi", and converted to methylation β-value, ranging from 0 to 1, with 0 being unmethylated and 1 being fully methylated, to represent the methylation level of each CpG site. Potential residue batch effects will be inferred from the data using a Surrogate Variable Analysis (SVA), and the ComBat algorithm will be used for correction. Rigorous quality-control criteria will be used for filtering at both the locus and sample levels. The final data will be supplied to the DNAm age estimation algorithms.

8.0. DATA HANDLING AND STATISTICAL CONSIDERATIONS:

8.1. Data Handling

8.1.1. The same protocols and procedures for data quality and control that are readily used for the NCI Community Oncology Research Program (NCORP) Research Base protocols currently being overseen by our office (which have accrued over 1,000 patients in the previous year) will be used for this study. Patients will fill out forms generated from RedCap and this information will be entered into RedCap (Section 9.5). Study personnel will perform SPPB and the scores will be entered into RedCap.

8.1.2. It is anticipated that allowing for the appropriate number of evaluable participants and by checking self-report measures for completeness, we will have a full complement of data. Every effort will be made to encourage and facilitate participants' completion of all questionnaires and all items on the questionnaires for each study assessment. In the event that missing data occur, every effort will be made to contact participants via phone and obtain the data or to find out why the questionnaires or items are missing. The reasons for missing data will be documented. Missing questionnaire items will be treated in accordance with the documented scoring procedures. Although it is very unlikely that missing values will not occur randomly, we will confirm their randomness. Multiple imputation¹¹³ will be applied to (1) give more accurate statistical tests and standard errors for key treatment effect parameters and to (2) give some indication of the sensitivity of the analyses to missing data. The causes and pattern of the missing data will be examined and taken into consideration in the design of future studies.

8.1.3. Data collected with the tablets and Garmin activity trackers will only be accessed by the following: 1) The research team including the exercise physiologist, 2) The treating physician and their designee, and 3) PointClick Care company. The research team and exercise physiologist will each have a username and password to access the tablets and devices. The PointClick Care company will have access to the data on the tablets. As discussed above, PointClick Care encrypts all PointClick Care data transferred between backend servers and the tablets. Communications to the server is validated by signed trusted server certificate. Data at rest is always encrypted. PointClick Care caches data on the tablet, and stores data on a PointClick Care server. On the tablet the cache in encrypted, the backend server hosts a Microsoft SQL Server database. The volume used by SQL Server is encrypted. Only the PointClick Care app, with a valid authentication key, can read this data. If the electronic data is breached, PointClick Care has a means to disable the PointClick Care app on a tablet. This feature only works, however, if the Tablet is connected to the server. We will also inform the study participants if the breach has occurred. Users are not able to exit the app from the tablet. If the tablet is lost or stolen, PointClick Care has a means to disable the PointClick Care app as soon as it is turned on. If the tablet is

broken, it will be replaced with a new one (all data within the tablet will be erased).

8.1.4. We are currently communicating with OPRA regarding the need for a data use agreement with the PointClickCare company.

8.2. Data Analysis and Sample Size:

8.2.1. Analysis Plan for Aim 1

Our planned sample size (N=15) will allow us to achieve thematic saturation. We will conduct and audio-record all interviews, which will be transcribed by a professional transcription service. We will analyze the qualitative data using grounded theory and constant comparative methods, with coding to structure data into categories and create groups according to the broader issues or themes.¹¹⁴ An audit trail of the coding activity will be kept. We will critically examine the data collection and analysis process and reach consensus on key themes from patient feedback to be used to adapt the intervention in preparation for Aim 2.

8.2.2. Analysis Plan for Aim 2

The feasibility of the GO-EXCAP Mobile App will be evaluated based on the following: a) Percentage of patients wearing the activity tracker and entering resistance exercise data into the mobile app and b) Percentage of patients performing both walking and resistance exercises during the study period days. Recruitment rates (percentage of patients who are approached and agree to enroll) and retention rates (percentage of patients who are enrolled and complete post-intervention assessments) will also be described

We will consider the intervention feasible if 1) \geq 70% of patients wear the activity tracker and enter resistance exercise data into the mobile app on at least 50% of the study period days, and 2) \geq 70% of patients performed both walking and resistance exercises on at least 50% of the study period days. We chose these criteria based on our previous mobile app study¹⁶ and on published exercise studies in older patients with AML.^{29,30} We will report percentage of adherence with 95% exact confidence interval (CI) calculated by the Clopper-Pearson method. We anticipate that about 20-30% of the participants will withdraw before post-intervention assessment due to rapid disease progression or death. These patients will not be included in the feasibility analysis because their withdrawals from the study are not related to the intervention. With 25 patients enrolled we anticipate at least 17 patients to be evaluable for our feasibility aims. When we estimate the percentage of adherence, a 95% CI will span approximately +/- 25%. For example, if we observe 12/17 (71%) patients complete the tasks, the CI will be 44-90%.

We will also tabulate the recruitment rates, retention rates, and intervention usability, and collect the reasons patient decline to be enrolled. In addition, we will evaluate the distribution and describe the following measures using descriptive statistics: 1) activity levels, 2) physical function (SPPB/vSPPB), 3) fatigue (BFI), 4) depression (CES-D Scale), 5) quality of life (FACT-Leu), and 6) Other geriatric assessment measures. Differences in activity levels, physical function, fatigue, depression, quality of life, and other geriatric assessment measures between pre- and post-treatment will be assessed using paired t-tests or Wilcoxon signed rank tests. Anticipated sample size of more than 12 patients with baseline and follow-up data will be sufficient to obtain the preliminary estimates of the outcomes measures.^{115,116}

Qualitative data from the exit interviews will be analyzed as per Aim 1. Interviews will be conducted, audio-recorded, and transcribed. Two trained "coders" will utilize a multi-step process using coding and content analysis, with coding to structure data into categories and creating groups according to the themes.¹¹⁴ We will identify themes that emerge within each content area. I will discuss these results with my study personnel and [name] every two weeks to critically examine the data collection and analysis process, provide critical feedback on emerging codes, and reach consensus on principal themes to be used to optimize the intervention. For every five patients, we will use the principal themes to optimize the intervention in an iterative process. We will identify patients who are not entering their daily steps or the resistance training data into the app. For these patients, we will elicit specific barriers and explore the relationship between these barriers and exercise adherence. We anticipate that the barriers to exercise adherence will be modifiable (e.g., symptoms, lack of selfmotivation, and lack of knowledge of the benefits of exercise) or non-modifiable (e.g., caregiving obligations, hospitalizations). The intervention will be optimized based on the following modifiable barriers, such as: a) Symptoms (e.g., fatigue, soreness): Monitor symptoms with automated self-management feedback and/or notification to the healthcare team; b) Lack of self-efficacy: Provide reassurance and motivational messages through the app; c) Lack of knowledge: Provide education on the benefits of exercise.

